**Prevention of Bone Loss after Acute SCI by Zoledronic Acid:
Durability, Effect on Bone Strength, and Use of Biomarkers to Guide Therapy**

Principal Investigator: [name], PhD
Northwestern University
[name]
[contact]
Email: [contact]

Study Drug: Zoledronic Acid

Funding Source: Department of Defense (DOD)

Initial version: 01 July 2014
Amendment 1: 26 November 2014
Amendment 2: 07 January 2015
Amendment 3: 12 March 2015
Amendment 4: 04 June 2015
Amendment 5: 13 January 2016
Amendment 6: 13 December 2016
Amendment 7: 20 March 2017
Amendment 8: 08 November 2017
Amendment 9: 28 June 2020

STUDY SUMMARY

Title	Prevention of Bone Loss after Acute SCI by Zoledronic Acid: Durability, Effect on Bone Strength, and Use of Biomarkers to Guide Therapy
Short Title	Effects of zoledronic acid on bone in acute SCI: Guide to therapy
Protocol Number	A-18350
IND/IND Holder	104662 / [name], PhD
Phase	Phase 2
Methodology	Randomized, Double-blind, Placebo-controlled
Study Duration	2 years
Study Center(s)	Single center: Northwestern University
Objectives	Identify an effective therapeutic approach to prevent or mitigate the loss of bone mass and bone strength after acute spinal cord injury.
Number of Subjects	60
Diagnosis and Main Inclusion Criteria	Acute spinal cord injury
Study Product(s), Dose, Route, Regimen	Zoledronic acid 5mg (NDC# 42023-0163-01) IV infusion
Duration of administration	15-30 mins, once a year (Total twice for entire study)
Reference therapy	Placebo, IV infusion
Statistical Methodology	A linear mixed-effects model with percentage-change from baseline to endpoint between active and placebo groups

CLINICAL PROTOCOL

Protocol Title: Prevention of Bone Loss after Acute SCI by Zoledronic Acid: Durability, Effect on Bone Strength, and use of Biomarkers to Guide Therapy/A-18350

Study Locations

The study will be conducted at the following locations:

Northwestern University Feinberg School of Medicine
Federalwide Assurance (FWA) Identification Number: FWA 00001549

Shirley Ryan AbilityLab (formerly Rehabilitation Institute of Chicago (RIC))
Federalwide Assurance (FWA) Identification Number: FWA 00001553

University of Calgary
Federalwide Assurance (FWA) Identification Number: FWA 00000810

The principal investigator for the study and at Northwestern University will be:

[name], PhD
Professor of Physical Medicine and Rehabilitation and Internal Medicine
[name]

1.1. Rationale

Spinal cord injury results in acute bone loss which is rapid and profound.

Spinal cord injury (SCI) results in marked acute loss of bone, primarily limited to those bony structures that are below the level of the neurologic lesion and non-weight-bearing, with little or no loss of bone at the spine and in bony structures that are supraspinal.^{1,2} The bone loss occurs rapidly, with the greatest decrease in bone density observed during the first 6-18 months after spinal cord injury, and is profound in magnitude, commonly being in the range of 15-30% at the hip, and potentially even higher at sites of less weight-bearing and of greater trabecular content below the hip.^{1,2} The degree of bone loss has been shown to be highly dependent on the degree of loading, with individuals having incomplete motor lesions and capable of some degree of weight-bearing having less bone loss than those with motor complete lesions.³ Lower extremity bone loss is similar in paraplegics and quadriplegics with similar motor function loss; upper extremity bone mass is unaffected in paraplegics but variably affected in quadriplegics, dependent on the degree of impairment of upper extremity function⁴. Age, weight and gender are important determinants of bone loss.³ Initially, bone mineral density (BMD) decline is reported to be most marked in areas rich in trabecular bone, with relative sparing of cortical bone ^{2,5-8} though recent studies from our group indicate significant acute loss of cortical bone as well ⁹ This enhanced rate of bone loss can be observed for between 2 and 5 years after acute SCI, at which time a new steady state is reached and bone resorption and bone formation become once again tightly coupled, but now at a new “set point” with bone mass that is 30-50% below the level prior to the injury.^{2,5-7} After this point in time, there is a much reduced rate of bone loss, with other secondary causes of bone loss, e.g., estrogen withdrawal, endocrinopathies, being potentially important contributors to further changes in bone status.

Loss of bone mass after acute SCI is paralleled by a marked decrease in bone strength.

Although reduction in bone mass after acute SCI has been well documented, there is an even more profound reduction in bone strength,^{9,10} assessed by finite element (FE) modeling. Bone strength is a multifactorial measure dependent not only on bone mass, but on parameters such as geometry, mineral distribution, material properties, and mode of loading. Unlike basic densitometry measures, FE models capture this information and account for the complex interaction between these factors. Research has consistently illustrated that information derived from FE models is associated with a substantial improvement in fracture strength prediction compared to DXA and QCT.^{11,12} Evidence from large fracture surveillance studies in able-bodied adults suggests that FE-predicted fracture strength is a better predictor of both prevalent¹³ and incident¹⁴ fractures when compared to DXA. Data from our group that has been published recently¹⁰ and detailed below provides further support to the greater magnitude in changes of estimating bone strength after acute SCI compared to either CT or DXA derived bone parameters alone.

Rapid bone loss after acute SCI is due to increased bone resorption and decreased bone formation.

The exact factors contributing to the rapid and profound bone loss after SCI have not been fully defined. Lack of normal weight-bearing is clearly an important component but likely not the sole contributor, with neural as well as endocrine dysregulation being hypothesized to potentially play other important roles. Thus, correction of weight-bearing alone may not be adequate to restore normal bone mass in this setting. Regardless of which factors are at play, when bone metabolism has been studied in the acute setting what has been most striking is the marked increase in bone resorption with elevated levels of bone resorption markers such as CTX and deoxypyridinoline, reflecting increased osteoclast activity.²¹⁻²³ Additionally, bone formation is down-regulated, undoubtedly due to diminished loading, with evidence of an inadequate bone formation osteoblastic response.^{1,23,24} The subsequent decrease in bone mass is coupled with a decrease in bone quality, with both cortical and trabecular bone being affected^{5,7,9} which has a major impact on bone strength.

Prevention of bone loss reduces risk of fracture.

Large epidemiologic studies have identified a number of risk factors for fracture in the general population including gender, age, family history of fracture, prevalent fracture, vitamin D status, and current bone mineral density.²⁵⁻²⁹ Because of the accelerated bone loss occurring in women at the time of menopause and their subsequent high risk of fracture, attention early on focused on looking for interventions to prevent this bone loss with the goal of reducing fracture risk. Initial efforts focused on estrogen³⁰ and other hormonal therapies, including calcitonin³¹, but over the past decade or more the predominant approach to the prevention and treatment of bone loss and osteoporosis has been the use of bisphosphonates.

Second and third-generation bisphosphonates (alendronate³², risedronate³³, ibandronate³⁴ and zoledronate¹⁸) have been rigorously tested in post-menopausal women with osteoporosis and demonstrated to be effective at not only reducing bone loss but also increasing bone mass as well as preventing vertebral, and in most instances, non-vertebral fractures in this population.³² Importantly, these studies also confirmed the epidemiologic data that highlighted the importance of both current BMD and pre-existing fracture as risk factors for subsequent fracture, identifying those at highest risk.

In contrast to the extensive data available in post-menopausal women regarding reduction in fracture risk with bisphosphonates, few fracture prevention studies have been undertaken in other high risk populations (older men, people receiving glucocorticoids) with a recent study demonstrating efficacy of zoledronic acid in preventing morphometric vertebral fractures in older men being a notable exception.³⁵ Nevertheless, bisphosphonates have been shown to increase BMD (or prevent bone loss after glucocorticoid use) in these settings and have been approved for the prevention of bone loss and the treatment of osteoporosis in these groups of individuals. No large studies of bisphosphonates have been undertaken in individuals with SCI, but smaller studies cited below have demonstrated the effectiveness of some bisphosphonates, administered immediately after acute SCI, in preventing bone loss and the subsequent development of osteoporosis.

1.2. Preliminary Data

Pilot study of zoledronic acid after acute SCI

Our recent research has focused on the use of intravenous zoledronic acid to prevent bone loss after acute SCI. Zoledronic acid is felt to represent an ideal anti-resorptive agent for acute SCI because it can be easily given in either an in-patient or out-patient setting (one 15 minute intravenous infusion), ensures compliance for long periods of time, does not require the strict early morning administration of oral bisphosphonates, and can be utilized in people who may not be able to remain sitting for a full half-hour after administration. As noted above, two limited studies have previously evaluated zoledronic acid after acute SCI;69,70 both demonstrated an initial response to treatment, with a significant reduction in bone loss compared to placebo with somewhat discordant results regarding longer-term efficacy. Our own pilot data support the efficacy of zoledronic acid to mitigate the acute loss of BMD that occurs after acute SCI.

We have completed a pilot, double-blind, randomized, controlled trial in which participants after acute SCI received either a single intravenous administration of zoledronic acid 5 mg or placebo and then were followed with DXA and serum bone markers at 3 months, 6 months and one year and at 6 monthly intervals thereafter.

Because of the concern of not treating individuals who demonstrated significant bone loss, we stipulated that if any participant were to demonstrate a decrease in BMD at any DXA site at 6 months after treatment of $>10\%$, that participant would be eligible for retreatment, in a blinded manner, with whichever treatment they did not receive at baseline, and then continue to be followed as above. This approach meant that if placebo treatment resulted in rapid bone loss of great magnitude, these participants would have the option of receiving active treatment. It also ensured that individuals receiving zoledronic acid at baseline would not receive a second infusion after 6 months, regardless of their change in BMD. This latter assurance was a consequence of an FDA request made upon review of our original protocol when submitting the IND for this study.

Fourteen participants were recruited from among in-patients admitted to the Rehabilitation Institute of Chicago over approximately a one year period. BMD changes determined by DXA demonstrated a rapid loss of bone in all of the placebo participants, with all reaching the 10% threshold of BMD loss at one region of interest by 6 months. All were offered retreatment but only 3 gave consent and these participants were then infused with zoledronic acid 5 mg and followed according to the original protocol. None of the participants initially treated with zoledronic acid reached the 10% threshold at 6 months; four of the seven participants treated initially with zoledronic acid are continuing to be followed beyond the 12 month time point in an observational longitudinal extension study to evaluate the duration of effect of zoledronic acid (Fig. 1).

[figure not shown]

Fig. 1. Subjects treated at baseline with either zoledronic acid (blue line) or placebo (red line); at 6 months, all placebo subjects had lost >10% BMD and were treated with zoledronic acid (dashed green line). BMD determined at times indicated.

Thus, our data add new information to the current literature by providing some, though limited, data regarding duration of the effect of a single infusion of zoledronic acid, and by exploring the consequences of delaying treatment to prevent bone loss. The value of retreatment after 1 year to maintain efficacy and the potential role of serum markers of bone metabolism to guide decisions regarding retreatment are currently unknown and have not been explored in these studies. Additionally, the effect of intervention with zoledronic acid on bone strength, not simply DXA-determined BMD, also has not been evaluated and should provide additional important information regarding efficacy of treatment and its durability.

Change in bone strength after acute SCI.

Bone strength was not evaluated in any of the participants in the pilot zoledronic acid study. However, in a parallel study of 10 SCI individuals, evaluated at the knee (proximal tibia and distal femur) by CT shortly after their acute injury and then 3 months later, we have seen dramatic decreases in both cortical and trabecular bone mineral content and volumetric bone mineral density⁷¹. Finite element (FE) analysis of these data has indicated an associated marked decrease in bone strength approximately 2.5 times greater than that observed for bone mineral density. Examination of the distal femur, done as part of the same study, showed very similar results.⁹ These data support the value of not only obtaining CT data in order to more accurately determine changes in BMD that is possible by DXA, where positioning and the presence of heterotopic ossification both pose significant concerns, but also to provide information which can be used to evaluate changes in bone strength, which may be an important consideration when recommendations regarding initiation of activities such as assisted weight-bearing are being considered during recovery.

2. Objectives and Specific Aims

The overall objective of this study is to define an effective therapeutic approach, using currently available medication, to prevent or mitigate the loss of bone mass and bone strength that occurs after acute spinal cord injury. Zoledronic acid is felt to represent an ideal anti-resorptive agent in this setting for the reasons outlined above. Additionally, treatment with zoledronic acid after SCI has been shown by us and others in studies of limited size and duration to demonstrate short-term efficacy in prevention of bone loss. However, the durability of the response to a single infusion of zoledronic acid is undefined, the need for repeat treatment has not been explored, the

consequences of delayed intervention with zoledronic acid are not known, and effects on bone strength have not been determined. Consequently, treatment after acute SCI to prevent bone loss is rarely, if ever, considered and is not the standard of care.

This study aims to provide a robust base of evidence to guide the use of zoledronic acid after acute SCI. This will be accomplished by undertaking a randomized, controlled clinical trial in which different treatment regimens of zoledronic acid will be compared with each other and with placebo.

The primary aims of the study and the associated hypotheses are:

AIM 1: To define the timing and frequency of administration of zoledronic acid 5mg infusion that will result in the optimal prevention of bone loss after acute SCI.

Hypothesis 1: In participants treated shortly after acute SCI with a single infusion of zoledronic acid, the mean loss of bone after both one year (Hypothesis 1a) and two years (Hypothesis 1b) at skeletal sites in the lower extremity (total hip, femoral neck, proximal tibia, distal femur) will be less than that determined for participants who received placebo. The primary hypothesis will focus on changes at the total hip site and the study powered accordingly.

The following additional hypotheses will also be addressed:

Hypothesis 1c: The effects of a single infusion of zoledronic acid after acute SCI will wane over time; retreatment with zoledronic acid after one year will result in greater maintenance of bone than a single infusion with zoledronic acid.

Hypothesis 1d: Initiation of treatment with zoledronic acid at one year after acute SCI in people not previously treated to prevent bone loss will still result in preventing further bone loss compared to no active bone-specific treatment; loss of bone mass that has occurred during the initial year without treatment will not be reversed, however.

To accomplish these objectives, we will undertake a 2 year, double-blinded, randomized, controlled trial. During the first year, participants will be randomized to either zoledronic acid 5 mg or placebo, and evaluated at 3, 6 and 12 months after infusion by DXA and CT imaging to determine changes in bone mass. At the 12 month time point, the participants in each of the treatment groups (zoledronic acid, placebo) will be re-randomized in a 1:1 ratio to receive either an infusion of zoledronic acid 5 mg or an infusion of placebo and followed during a second year of study. During year 2, participants will be evaluated at 6 and 12 months after re-infusion by DXA and CT imaging to determine changes in bone mass. (Subjects weighing less than 40 kg and assigned to receive study drug will be administered a reduced dose of 2 mg instead of 5 mg.)

AIM 2: To evaluate the use of serum markers of bone metabolism to guide therapeutic decisions of timing and need for retreatment with zoledronic acid after acute SCI.

Hypothesis 2: Serum levels of markers of bone resorption will be elevated after acute SCI and suppressed by zoledronic acid infusion. Recovery of bone markers to high levels will correlate

with continued bone loss and provide a signal indicating the need for additional anti-resorptive intervention.

Serum will be obtained at each of the imaging visits and biomarkers of bone metabolism will be measured and correlated with bone changes determined by DXA and CT.

AIM 3: To evaluate the effects of zoledronic acid in mitigating loss of bone strength that occurs after acute SCI.

Hypothesis 3: Changes in bone strength determined by finite element analysis will be greater than those seen in measurement of bone mass by either DXA or CT, with particular loss of strength noted at the distal femur and proximal tibia.

FE analysis utilizing data from the CT imaging will be undertaken to provide estimates of bone strength.

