Levels of serum markers of bone metabolism will provide useful information regarding appropriate timing for retreatment. Mean levels of serum markers of bone resorption will be significantly reduced after each infusion of zoledronic acid and will increase again at the end of one year but will not reach baseline. Retreatment with zoledronic acid will reduce mean serum marker levels of bone resorption again whereas the group given placebo will have a return of mean serum levels of resorption markers close to the baseline value. Increases in bone resorption markers will presage further loss of bone.

[figure not shown]
CT analyses and bone strength.

CT analysis will provide additional information regarding differential bone loss at trabecular and cortical sites at both hip and knee, and FE analysis of bone strength will demonstrate greater differences between and among groups than seen with DXA and CT evaluation at all skeletal sites.

3. Study Design

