3.1. Overview

This is a 2 year, randomized, double-blind placebo-controlled study of zoledronic acid to evaluate its efficacy and safety for the prevention of bone loss and maintenance of bone strength in individuals with recent onset SCI (see diagram below). Subjects will be randomized at the baseline visit to receive either zoledronic acid or placebo. At the end of the first year of the study, each treatment group will be re-randomized to either zoledronic acid or placebo to evaluate the durability of response to zoledronic acid and the utility of serum bone markers to guide therapeutic decision making. DXA imaging, CT imaging of knee and bone markers will be obtained at baseline, 3 months, 6 months, 12 months, 18 months and 24 months. CT imaging of hip will be obtained at baseline, 6 months, 12 months, and 24 months.

3.2. Centers and enrollment goal:

This will be a single center study. 60 subjects meeting inclusion and exclusion criteria will be enrolled at Northwestern University. University of Calgary (UC) will act as a site for de-identified data analysis of CT scans. No subjects will be enrolled and no visits will take place at UC.

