### ***Exploratory Analyses***

Serum bone markers (i.e., P1NP, BSAP, CTX) and additional CT bone biomarkers, measured at 3, 6, 12 and 24 months will be evaluated using a similar approach as for the primary analyses – linear mixed effects model. A compressive strength index (CSI; g2/cm4) and a torsional strength index (TSI; cm3) will be computed for each skeletal region. Finally, CT-based finite element analysis will be used to predict stiffness and strength at the hip, distal femur, and proximal tibia.

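### The retreatment-guidance half of Hypothesis 2 has no analysis that can support it: the one stated link between markers and bone is a correlation with no time order and no adjustment for treatment

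*Protocol*

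**What the plan says.** Marker-guided therapy is in the trial's title, and Aim 2 is one of three aims that Protocol section 2 calls primary. Its purpose is to use markers "to guide therapeutic decisions of timing and need for retreatment with zoledronic acid after acute SCI".

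Hypothesis 2 has two halves:

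- Description: "Serum levels of markers of bone resorption will be elevated after acute SCI and suppressed by zoledronic acid infusion".
- Guidance: recovery of the markers is to correlate "with continued bone loss and provide a signal indicating the need for additional anti-resorptive intervention".

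Protocol section 2.2 adds a claim about time order: "Increases in bone resorption markers will presage further loss of bone". Protocol section 3.1 gives "the utility of serum bone markers to guide therapeutic decision making" as one purpose of the month-12 re-randomisation, and the SAP Overview repeats it.

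On analysis, the protocol says under Aim 2 that "biomarkers of bone metabolism will be measured and correlated with bone changes determined by DXA and CT". Protocol section 14 contains no marker analysis and defers to the SAP. The SAP's hypotheses are 1a to 1d only. It lists P1NP, BSAP and CTX as exploratory endpoints and says that they "will be evaluated using a similar approach as for the primary analyses", that is, with a linear mixed-effects model, for markers "measured at 3, 6, 12 and 24 months". The Analysis Plan Summary table has no marker row.

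**The concern.** The primary model in the SAP compares treatment groups on a bone outcome. A similar approach for CTX makes CTX the outcome. That shows what zoledronic acid does to the marker, but not whether the marker says anything about later bone loss or about who gains from a second infusion.

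Only the Aim 2 correlation links marker to bone. Treatment is expected to move both in a favourable direction, so treated participants would tend to have low CTX and little loss, and placebo participants the reverse. If the arms are put together, that alone produces a correlation. Nothing in the text rules this out, and nothing requires the marker to be measured before the bone change. A claim that markers guide retreatment could then rest on an association created by the randomised treatment.

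**Working it through.** **The plan's own figure.** The documents give no sample size or power for Aim 2. The design figure behind N = 60 is a detectable BMD difference of d = 0.74 with 30 per group and 80% power (Protocol section 14.3). A two-sided t-test at 0.05 gives 0.736, so it reproduces.

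**Inputs.**

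- BMD effect, upper value: left total hip in Table 2. The difference is −3.40 − (−13.83) = 10.43 points. The pooled SD is √((3.51² + 2.01²)/2) = 2.86, so d = 10.43/2.86 = 3.65.
- BMD effect, lower value: the same 10.43 points over 9.02, the largest hip SD, which section 14.3 uses as its conservative SD for all sites. This gives 10.43/9.02 = 1.16. It is not the effect size of any row of Table 2.
- CTX effect: not in the documents. Assumed to be 1.0 to 1.5 within-arm SD, with 0.5 to 2.0 as a wider range.

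**Correlation created by treatment alone.** With two equal arms and no link within either arm, the pooled correlation in absolute size is the product of two terms of the form d/√(d² + 4), one for the marker and one for bone.

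- Low end: CTX 1.0 gives 0.447 and BMD 1.16 gives 0.502. The product is 0.22.
- High end: CTX 1.5 gives 0.600 and BMD 3.65 gives 0.877. The product is 0.53.

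With t = r√58/√(1 − r²) at n = 60:

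- r = 0.22: t = 1.72, p = 0.09
- r = 0.53: t = 4.76, p < 0.001

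**How often p < 0.05 would occur with no within-arm link** (Fisher z, n = 60; it should be 5%):

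| BMD effect | CTX 0.5 | CTX 1.0 | CTX 1.5 | CTX 2.0 |
|---|---|---|---|---|
| 0.74 | 9% | 22% | 36% | 47% |
| 1.0 | 13% | 33% | 55% | 70% |
| 3.9 (protocol's pilot hip value) | 38% | 89% | 99% | about 100% |

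**Adjusting for arm.** In simulation (20,000 runs per setting), the arm-adjusted correlation averages about 0 and is significant in 4.8% to 5.1% of runs.

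**Over two years, the form of the adjustment matters.** Participants who switch at month 12 change treatment state within their sequence, so additive terms for sequence and visit do not absorb the treatment effect. In simulations with no marker-bone link, additive adjustment still rejected about 7% to 47% of the time, depending on the assumed effects. Sequence-by-visit terms gave about 4% to 6%.

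**What an interaction could detect.** The table gives the difference in slopes detectable with 80% power at two-sided 0.05, in residual SD of bone change per SD of marker.

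| Comparison of second treatments | Full numbers | After 20% dropout |
|---|---|---|
| Zoledronic-acid-first group only | 1.06 (15 v 15) | 1.20 (12 v 12) |
| Both first-year groups | 0.74 (30 v 30) | 0.83 (24 v 24) |

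**The case against.** Four points on the other side have weight.

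- **Pooling is not written.** A reader might infer that the plan prescribes a simple correlation over all participants. It does not: one sentence in the aims section says correlated and leaves the rest open. Hypothesis 2 speaks of suppression and then recovery, which can be read as treated participants followed over time, and a within-arm correlation would not carry the artefact. This stands. The gap is that the text neither requires nor excludes pooling. Even a within-arm correlation would show prognosis only, not who benefits from retreatment.
- **Part of Aim 2 is covered.** A reader might infer that Aim 2 as a whole cannot be answered. The SAP's mixed model can address suppression and rebound of the markers, which is the first half of Hypothesis 2. Only the guidance half lacks an analysis.
- **Markers are exploratory in the SAP.** They have no stated alpha and no decision rule, and the primary endpoint is untouched. This limits the consequence. It does not remove it, because the title, Aim 2 and the SAP Overview still promise marker-guided therapy.
- **The size is uncertain.** The CTX effect is assumed. At the low end of the main range the induced correlation would not be significant (p = 0.09), and at the design's d = 0.74 the chance of a false finding is 9% to 47%. So a spurious result is possible, not certain.

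**Conclusion.** The concern holds for the guidance half of Hypothesis 2. No analysis in either document places the marker before the bone change, separates it from treatment, or uses the re-randomisation to ask whether marker level modifies the effect of the second infusion.

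If arms were pooled, treatment alone would give a correlation of about 0.22 to 0.53. This rests on assumed CTX effects of 1.0 to 1.5 SD, hip BMD effects of 1.16 to 3.65 SD, equal arms, n = 60 and no within-arm link.

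The documents do not support saying that pooling is planned or that a false claim is inevitable. The gap lies in the analysis plan, not in the data. Markers are scheduled at every DXA and knee CT visit, including month 18, and are drawn before the second infusion. The SAP should be changed, but confidence in the primary result is not affected.

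**What to change.** Amend the SAP's Exploratory Analyses section and label all of this exploratory.

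1. **Prognosis.** Replace the correlation with a lagged model. Regress percent change in total-hip aBMD (and, separately, knee Int.vBMC) from visit t to the next imaging visit on log CTX at t, for the intervals 3–6, 6–12, 12–18 and 18–24 months. Include treatment sequence-by-visit terms (not sequence plus visit), BMD at t (for the knee model, Int.vBMC at t) and a participant random effect. This needs the month-18 markers, which the SAP's list of visits omits although Protocol section 3.6 and the SAP Overview include them. Interpret the CTX coefficient as prognosis only.
2. **Retreatment guidance.** Add the interaction of the month-12 pre-infusion marker with the second randomised treatment on bone change from month 12 to month 24, adjusted for first-year treatment. State that with about 15 per group only large interactions are detectable.
3. **Month-6 cut-off.** Protocol section 10 censors further data for participants who reach the bone-loss cut-off, and those who then take the opposite treatment are not re-randomised. The SAP is silent on this. State that their intervals after month 6 are censored as the protocol says, and that participants who cross over at month 6 are not in the interaction analysis. Report how many are affected, since this removes the fastest losers.

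The cost is SAP wording and a few extra models on data already scheduled, with no new visits or participants. The association will probably look weaker than a pooled correlation. The 3–6 month interval will be thinner than the others, because month-3 visits may be held by phone (Protocol section 7).
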